## IRB Minimal Risk Protocol Template

**Note: If this study establishes a human specimen repository (biobank) for research purposes, do not use this template. Use the Mayo Clinic Human Specimen Repository Protocol Template found on the IRB home page under Forms and Procedures at <http://intranet.mayo.edu/charlie/irb/>**

**First-time Use:** Use this template to describe your study for a new IRB submission.

1. Complete the questions that apply to your study.
2. Save an electronic copy of this protocol for future revisions.
3. When completing your IRBe application, you will be asked to upload this template to the protocol section.

**Modification:** To modify this template after your study has been approved:

1. Open your study in IRBe. Click on the study 'Documents' tab and select the most recent version of the protocol. Save it to your files.
2. Open the saved document and activate "Track Changes".
3. Revise the protocol template to reflect the modification points , save the template to your files
4. Create an IRBe Modification for the study and upload the revised protocol template.

### Purpose

Hypothesis: An electronic nose can discern breath profiles between fasting and non-fasting individuals

Aims, purpose, or objectives: In patients undergoing endoscopic procedures, there currently is not a non-invasive process to assess whether the patient presents in a fasting state which is required for moderate sedation or anesthesia-assisted endoscopy. With the increased prevalence of type 2 diabetes and its associated comorbidity of gastroparesis which causes delayed gastric emptying, this may present retained food in the stomach even in individuals who comply to standard fasting protocols.

In non-fasting individuals, the risk of a sedation related complication such as aspiration increases and often the procedure must be aborted and repeated on another day following more prolonged fasting and medication administration. This adds to increased cost and delay to patient care.

We propose a mechanism by which we can quickly screen and assess for fasting and non-fasting states in individuals scheduled for routine endoscopy by utilizing a non-invasive breath analyzer called an electronic nose by which through pattern recognition we analyze electronic changes in exhaled volatile organic compounds interfacing with an electronic sensor that creates an electronic signature, or smell-print that distinguishes the fasting and non-fasting states.

Background (*Include relevant experience, gaps in current knowledge, preliminary data, etc.*): We eNose Company (eNose B.V., Zupten, NL), who will supply the electronic nose apparatus called the Aeonose device. This is a handheld, portable battery operated unit with a built in sensor that allows for data collection at the point of care with the subject breathing directly into the apparatus. The technology which is based on the prior commercially available Diagnose which was CE marked, and the Aeonose has already been utilized in large studies in breath analysis for head and neck cancer screening, tuberculosis screening, and is nearing commercialization by the eNose Company.

We have demonstrated experience working with the eNose Company in our study Identification of *C. difficile* infected stool by electronic nose using a device (Aetholab) with the same sensor technology (14-001369).

Preliminary studies show that signal separation can be detected within as few as 50 signals of 25 positive and 25 negative for training. A maturation process of pattern recognition occurs with 200 signals, 100 positive and 100 negative respectively. This is an initial pilot which can be expanded to the scale of a full study pending promising results. As we will be collecting positive and negative signals from the same patients, we anticipate subject numbers half that of the required signal training numbers.

#### **Subject Information** – charts, records, images, or specimens are considered ‘subjects’

*Target accrual is the proposed number of subjects to be included in your study at your site. “Subjects” may include Mayo Clinic charts, records, or specimens, and/or charts, records, or specimens received at Mayo Clinic from external sources for collaborating analysis by the investigator under this IRB application:*

Target accrual: 1000 patients

Subject population: Any outpatient adult individual undergoing elective upper endoscopy who consents to study participation

Inclusion Criteria:

1. English speaking
2. Adult (18+) patient undergoing scheduled elective outpatient upper endoscopy
3. Willing and able to consent to research protocol
4. Fasting as required per routine instruction for endoscopy or non- fasting adults accompanying the patient who are able to provide informed consent
5. Able to breath for approximately 5 minutes pre procedure into the Aeonose device with a nose-plug on

Exclusion Criteria:

1. Non-fasting per protocol, or known to have had food or drink outside of routine protocol
2. Non-English speaking
3. < 18 years of age
4. Unable or unwilling to consent to research protocol
5. Inability to tolerate Aeonose breathing (such as those with claustrophobia, anxiety, nasal trauma, etc.)
6. Use of antibiotics or systemic immunosuppressants within three months prior to the date of endoscopy (intranasal and inhaled steroids are allowed)
7. Any prior chemotherapy for esophageal cancer
8. History of squamous cell carcinoma
9. History of gastric or esophageal surgery
10. Per PI discretion, any current medical problem that could alter intended study data collection.

Yes  No Will a Certificate of Confidentiality (COC) be obtained from NIH? If yes,

Who is obtaining the COC: Mayo Clinic investigator, study sponsor, other:

Explain why a COC is needed:

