## Study Design

Methods: *Describe, in detail, the research activities that will be conducted under this protocol:*

Fasting individuals undergoing upper endoscopy in the gastroenterology unit or non-fasting adults accompanying the patients will be enrolled for participation in Aeonose pre-procedural breath testing. These include elective inpatient procedures which have high risk of gastric content retention, but also have increased health risks due to active comorbidities.

Individuals consenting to participation of this study will be asked to provide a breath analysis using the Aeonose per standard acquisition protocol which spans 5 minutes of which the individuals breaths normally through a sterile disposable mouthpiece with sterile disposable air filters for 5 minutes during signal acquisition while wearing a nose plug. This may be completed prior to their endoscopic procedure.

The signals generated from each subject consist of a de-identified electronic breath-print will be analyzed by the investigators and the aggregate results matched using pattern recognition techniques to localize into fasting and non-fasting states. For the pilot portion of this study, the primary outcome is to establish separation of these signals in the initial cohort.

**Resources:** *Describe the available resources to conduct the research (personnel, time, facilities, mentor commitment, etc.):*

The lab group and study team consists of a full time laboratory researcher, gastroenterology clinical investigator fellows, and clinical research coordinators to support the study. The lab is based in the Alfred Main laboratory space. The lab group has already received on-site training by the eNose Company in the operation of the Aeonose. One Aeonose unit is immediately available for dedicated use towards this project and a sufficient supply of disposables (filters and mouthpieces) is already in stock for this project. The eNose Company who is a collaborating partner has dedicated further resources (more Aeonose units and disposables) as needed.

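### Eligibility rules conflict on non-fasting companions; on the evident reading, with an intake-based label, fasting state in the full study cannot be separated from patient/companion role

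*Combined protocol and SAP*

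**What the plan says.** **Who may enter.** Under Subject Information, the population line reads "Any outpatient adult individual undergoing elective upper endoscopy who consents to study participation". Inclusion Criterion 2 asks for an "Adult (18+) patient undergoing scheduled elective outpatient upper endoscopy". Inclusion Criterion 4 accepts people who fasted as instructed or, as the alternative, non-fasting "adults accompanying the patient who are able to provide informed consent". Exclusion Criterion 1 removes anyone "Non-fasting per protocol, or known to have had food or drink outside of routine protocol" and makes no exception for companions. Study Design, Methods, sides with Inclusion Criterion 4: "Fasting individuals undergoing upper endoscopy in the gastroenterology unit or non-fasting adults accompanying the patients will be enrolled for participation".

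**How many.** The Power Statement (Statistical Considerations) plans 200 fasting and 200 non-fasting individuals with an accuracy aim above 85%, then a blinded validation group of 50 and 50. The pilot has 25 subjects, against a stated minimum of 25 positive and 25 negative samples.

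**How sampled.** The Background, where it gives signal numbers, says that both kinds of signal come from the same patients, so subjects number half the signals. Methods says "Individuals consenting to participation of this study will be asked to provide a breath analysis using the Aeonose" and schedules no second test. Inclusion Criterion 5 places the test before the procedure.

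**What the label means.** No section defines it. Purpose raises food retained in patients who complied with fasting, and Methods mentions inpatients at high risk of retained contents. The stated use is to screen people booked for endoscopy.

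**The concern.** A classifier can be credited with detecting fasting only if fasting is not a stand-in for something else. Patients and companions may differ in illness, medication and preparation for the procedure, any of which could affect breath. If all fasting subjects are patients and all non-fasting subjects are companions, a model that learns who is a patient and nothing about food scores exactly as if it had learned fasting.

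The blinded validation group would not expose this, because it has the same structure. The chart review and the secondary endpoint on influencing factors would not either, because no analysis can separate two variables that take identical values in every subject. What is at stake is the meaning of the primary endpoint, and whether anything is learned about a patient who arrives having eaten.

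**Working it through.** **1. Eligibility, group by group.**

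| Group | Literal reading | Evident reading (Inclusion 2 and Exclusion 1 bind patients only) |
|---|---|---|
| Patient, fasted as instructed | eligible | eligible |
| Patient known to have eaten | barred (Inclusion 4, Exclusion 1) | barred |
| Companion, not fasting | barred (Inclusion 2, Exclusion 1) | eligible |
| Companion, fasting | barred (Inclusion 2) | not provided for in Methods |

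The literal reading admits no *known* non-fasting person, against a planned 200 + 50 = 250. The antibiotic and immunosuppressant criterion ("Use of antibiotics or systemic immunosuppressants within three months prior to the date of endoscopy") also uses a date that a companion does not have, which suggests that the list was written for patients.

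**2. Aliasing in the full study.** Take the evident reading and a label by reported intake. For training, form a design matrix with an intercept, fasting state (200 ones, 200 zeros) and role (the same 200 ones and 200 zeros). The last two columns are identical, so the rank is 2 of 3 and the two effects are not separable. The 50 + 50 validation group has the same structure.

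**3. If the label follows stomach contents.** Compliant patients with retained food join the non-fasting class, so the aliasing among patients is partial. No endoscopy is described for companions, so they could still be labelled only by intake.

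**4. The pilot.** The plan's own arithmetic reproduces under paired sampling: 25 subjects × 2 samples = 50 = 25 + 25. With one test each, 25 subjects give 25 samples, half the stated minimum. With 25 subjects sampled in both states, a design with 25 subject terms plus fasting has rank 26 of 26, so fasting is identifiable within subject.

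**5. How misleading could the aliased result be?** This is illustration only. Let r be the accuracy with which breath reveals role, assumed equal in patients and companions. The documents do not give r, so a range is shown. With no fasting signal, apparent fasting accuracy equals r. The chance of 86 or more correct out of 100 is P(Binomial(100, r) ≥ 86):

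| r | Probability |
|---|---|
| 0.70 | 0.02% |
| 0.80 | 8% |
| 0.85 | 46% |
| 0.90 | 93% |
| 0.95 | over 99.9% |

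The cut of 86 borrows the Power Statement's overall aim; no pass mark is stated for validation.

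**6. Partial crossing.** If m of the 50 non-fasting validation subjects are patients, the role-only model's expected accuracy is r(1 − m/100) + (1 − r)(m/100). At r = 0.90 this gives 90% (m = 0), 86% (m = 5), 82% (m = 10) and 70% (m = 25). The bias shrinks gradually, with no safe cut-off.

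**7. Which summary reveals the problem.** Pooled accuracy among patients does not. With 50 fasting patients and m non-fasting ones, the role-only model gives (50r + m(1 − r))/(50 + m). At m = 5:
- r = 0.90: (45 + 0.5)/55 = 82.7%
- r = 0.95: (47.5 + 0.25)/55 = 86.8%

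That figure is mostly specificity. The same model's sensitivity in non-fasting patients is only 1 − r, that is 10% and 5%, so sensitivity must be shown separately.

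**The case against.** **The plan already intends same-patient sampling.** The Background says so and the pilot numbers fit. This largely stands for the pilot. Exclusion Criterion 1 does not defeat it: it is an entry rule, and a patient could enter fasting and give a fed sample later. Nor does the Methods wording clearly limit each person to one test. What remains is that the second sample has no stated timing, Inclusion Criterion 5 says before the procedure, and the Power Statement counts separate individuals in the full study.

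**The label may follow stomach contents.** Purpose and the inpatient sentence in Methods may point that way. The documents do not settle it, so complete aliasing has to be stated as conditional.

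**The probabilities prove little.** They run from 0.02% to over 99.9% with an unknown r. On an equal-variance normal model, reaching 85% on role alone needs Φ(d/2) = 0.85, a patient–companion difference of about d = 2.07 SD. This stands: the figures show what is possible, not what is likely. Non-identifiability does not depend on r.

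**Stronger readings that the documents do not support.** A reader might infer that the non-fasting class is empty. That follows only for known non-fasting people on the literal reading, which Methods contradicts; under a stomach-contents label, compliant patients with retained food remain eligible. A reader might also infer that the pilot is confounded in the same way, or that the device would reach its 85% aim on role alone. The Background tells against the first, and nothing in the documents gives the size of any role difference.

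**Conclusion.** The point holds in conditional form and should be fixed before full-study enrolment. The conflict between Inclusion Criteria 2 and 4, Exclusion Criterion 1 and Methods is on the page and rests on no assumption.

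Complete aliasing in the 200 + 200 and 50 + 50 individuals rests on two: that the patient-only rules bind patients only, and that the label follows reported intake. Under both, overall accuracy cannot be read as detection of fasting, and performance in patients who have eaten is not estimated. With a stomach-contents label the aliasing is partial; with same-patient sampling it is removed. Once enrolment follows the completely aliased pattern, analysis cannot repair it.

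**What to change.** 1. Write eligibility separately for patients and companions, exempting companions from Inclusion Criterion 2 and Exclusion Criterion 1.
2. Break the aliasing in the full study where possible. Enrol fasting companions. Let patients known to have eaten give a breath sample with no change to their care. Carry the Background's paired sampling through Subject Information, Methods and the Power Statement, say when each sample is taken, and keep both samples of one person in the same set (training or validation).
3. State whether the label follows reported intake or stomach contents at endoscopy.
4. Record patient/companion status for every subject. Report sensitivity in non-fasting patients and specificity in fasting patients separately, each with an exact CI. Do not substitute pooled patient-only accuracy.
5. If few or no non-fasting patient samples are obtained, state that overall accuracy cannot be distinguished from patient-versus-companion discrimination.

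**Cost:** an eligibility amendment, a written label definition, one recorded field, and a second test of about 5 minutes for those sampled twice. The number of patients who arrive having eaten is not given and may be small, so sensitivity in patients may be imprecise: exact 95% CIs are 28–99% for 4/5, 44–97% for 8/10 and 59–93% for 20/25.

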## Study Design

Methods: *Describe, in detail, the research activities that will be conducted under this protocol:*

Fasting individuals undergoing upper endoscopy in the gastroenterology unit or non-fasting adults accompanying the patients will be enrolled for participation in Aeonose pre-procedural breath testing. These include elective inpatient procedures which have high risk of gastric content retention, but also have increased health risks due to active comorbidities.

Individuals consenting to participation of this study will be asked to provide a breath analysis using the Aeonose per standard acquisition protocol which spans 5 minutes of which the individuals breaths normally through a sterile disposable mouthpiece with sterile disposable air filters for 5 minutes during signal acquisition while wearing a nose plug. This may be completed prior to their endoscopic procedure.

The signals generated from each subject consist of a de-identified electronic breath-print will be analyzed by the investigators and the aggregate results matched using pattern recognition techniques to localize into fasting and non-fasting states. For the pilot portion of this study, the primary outcome is to establish separation of these signals in the initial cohort.

**Resources:** *Describe the available resources to conduct the research (personnel, time, facilities, mentor commitment, etc.):*

The lab group and study team consists of a full time laboratory researcher, gastroenterology clinical investigator fellows, and clinical research coordinators to support the study. The lab is based in the Alfred Main laboratory space. The lab group has already received on-site training by the eNose Company in the operation of the Aeonose. One Aeonose unit is immediately available for dedicated use towards this project and a sufficient supply of disposables (filters and mouthpieces) is already in stock for this project. The eNose Company who is a collaborating partner has dedicated further resources (more Aeonose units and disposables) as needed.

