### Statistical Considerations

**Power Statement:** This initial portion of the study is a pilot/feasibility study with 25 subjects. Based on the experience of the eNose company who will be providing analytical and statistical support in pattern recognition a minimum of 25 positive and 25 negative samples are needed to start to discern separation. In other models, 100 positive and 100 negative training set is needed to create a robust diagnostic model. Further subjects beyond that, such as in multiple sites further fine tune the diagnostic model through pattern recognition learning algorithms (artificial neural networks).

Sample size calculations using 80% power with a 5% level of significance, assuming a 50% fasting / non-fasting prevalence, with a test with a minimum sensitivity and specificity of 80% suggests that about 450 patients are required to achieve statistical power. We will obtain 200 fasting and 200 non-fasting individuals to achieve aim for an accuracy greater than 85%. An additional blinded test group of 50 fasting and 50 non-fasting subjects will be used for model validation. Statistical modeling for training and validation will be performed by the eNose Company using artificial neural networks for pattern recognition as they have been already providing this support through our research collaboration. We will perform descriptive statistics of patient demographics and characteristics

**Data Analysis Plan:** The eNose company has proprietary expertise in digital signal processing, artificial neural network pattern recognition techniques, the basis which is on published algorithms and established methodologies. The eNose company in collaboration with the investigators will receive encrypted, de-identified digital signatures for training and create a diagnostic model. If the pilot study proves fruitful, this protocol will be expanded into a full study by increasing the enrollment to a full study.

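### The protocol does not settle whether non-fasting breath comes from the same patients or from their companions; with companions, fasting state and role cannot be told apart

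*Combined protocol and SAP*

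**What the plan says.** **Same-person scheme.** The Background text under Purpose says that, by "collecting positive and negative signals from the same patients, we anticipate subject numbers half that of the required signal training numbers". The pilot in Statistical Considerations agrees: "This initial portion of the study is a pilot/feasibility study with 25 subjects", alongside "a minimum of 25 positive and 25 negative samples are needed to start to discern separation". The subject population line under Subject Information also names endoscopy patients only: "Any outpatient adult individual undergoing elective upper endoscopy who consents to study participation".

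**Separate-person scheme.** Study Design, Methods: "Fasting individuals undergoing upper endoscopy in the gastroenterology unit or non-fasting adults accompanying the patients will be enrolled". Inclusion criterion 4 repeats this choice. The Methods describe a single 5-minute acquisition and no fed-state visit. For the full study, Statistical Considerations counts people in each state: "We will obtain 200 fasting and 200 non-fasting individuals to achieve aim for an accuracy greater than 85" per cent, then "An additional blinded test group of 50 fasting and 50 non-fasting subjects will be used for model validation".

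**Eligibility.** Inclusion criterion 2 requires a patient scheduled for elective outpatient endoscopy, and exclusion criterion 1 bars anyone who is not fasting. Read literally, both shut out the companions whom criterion 4 admits.

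**Endpoint.** The primary endpoint under Endpoints is whether the device can tell fasting breath from non-fasting breath.

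**The concern.** The two schemes answer different questions, and the protocol does not choose between them.

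If patients supply every fasting signal and companions every non-fasting signal, the classifier is trained on a label that is also patient-versus-companion status. The two groups may differ in illness, medication and preparation for the procedure. The protocol itself expects such influences: the Methods mention inpatients with active comorbidities, and the chart review looks for medication, disease and other factors that alter breath. A network that learned only those differences would still score well in training and in the blinded test group.

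The Purpose section also expects some compliant patients to retain food. True gastric state may therefore differ from the label given at recruitment, yet nothing in the protocol relabels them.

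At stake is what a good accuracy figure would mean. The pilot is affected too: its stated outcome is signal separation, which role alone could produce, and expansion to the full study depends on its results.

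**Working it through.** **1. Which scheme do the plan's own counts follow?** Inputs: the halving rule (Purpose, Background) and the counts in Statistical Considerations. Paired headcount = signals / 2; separate headcount = signals.

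| Stage | Signals | People if paired | People if separate | Protocol states |
|---|---|---|---|---|
| Pilot | 25 + 25 = 50 | 50/2 = 25 | 50 | 25 subjects |
| Training, full study | 200 + 200 = 400 | 400/2 = 200 | 400 | 200 + 200 individuals |
| Blinded test | 50 + 50 = 100 | 100/2 = 50 | 100 | 50 + 50 subjects |
| Full study, total | 500 | 250 | 500 | 500 |

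The pilot figure is reproduced only at 50/25 = 2 signals per person, taking 25 as a headcount. The full-study figure is 500/500 = 1 signal per person. The Methods paragraph ends by stating the pilot's outcome, so it governs the pilot too, and the conflict cannot be read as one scheme for the pilot and another for the full study.

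**2. What follows if companions are the non-fasting source?** That the 200 and the 50 non-fasting people are companions is inferred from the Methods and inclusion criterion 4; Statistical Considerations does not say so.

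| | Fasting patient | Fasting companion | Non-fasting patient | Non-fasting companion |
|---|---|---|---|---|
| Training | 200 | 0 | 0 | 200 |
| Test | 50 | 0 | 0 | 50 |

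Code state as 1 for non-fasting and role as 1 for companion. The two columns are identical, so their correlation is 1.0 and the design matrix (intercept, state, role) has rank 2 of 3 in both sets. Only the combined effect of state and role can be estimated. No covariate adjustment recovers the separate effects, and blinding does not change the cells.

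Nothing else in the protocol fills the empty cells. The chart review concerns the patient's chart. The planned description is also limited to patients: "We will perform descriptive statistics of patient demographics and characteristics". The secondary endpoint on influencing factors adds no fasting companions and no fed patients.

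**3. Is pairing clean?** Inclusion criterion 5 places the breath test before the procedure, and exclusion criterion 1 bars non-fasting patients. With fasting instructions unchanged, a same-day non-fasting breath could only come after the procedure. For 50 patients with fasting always first, the matrix (50 person indicators, state, order) has 52 columns and rank 51, so state and order are not separable. State would usually coincide with sedation as well.

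**4. Illustration only.** Assume no fasting effect, one normal marker shifted by d standard deviations between roles, and a pass rule of more than 85 of 100 test subjects correct. Both d and the rule are assumptions: the protocol ties 85% to the 200 + 200 individuals and sets no criterion for the test group. Accuracy = Φ(d/2); chance of passing = P(X > 85) with X ~ Bin(100, accuracy).

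| d | Expected accuracy | Chance of passing |
|---|---|---|
| 1.0 | 69% | <0.1% |
| 1.5 | 77% | 2% |
| 2.1 | 85% | 49% |
| 2.5 | 89% | 90% |

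A simulated linear classifier (10 features, 200 + 200 training, 50 + 50 test, 500 runs, no fasting effect) agrees: at d = 2.5, mean accuracy was 89% and 87% of runs exceeded 85%. The same models applied to patients only scored about 50%.

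**The case against.** **The empty cells are inferred.** No table of role by state appears, and the sample-size sentence speaks of about 450 patients at 50% prevalence, which suggests patients in both states. This stands as a limit on certainty. It is also further evidence of the contradiction, since the Methods and inclusion criterion 4 name companions as the non-fasting group.

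**A mixed reading is possible.** Patients might give both signals while companions add more non-fasting ones, which would bring the correlation below 1.0. But companions giving one signal each would break the rule that subjects are half of signals, and the text does not establish this reading.

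**The number of breaths is not stated.** The Methods describe a breath test without capping it at one per person, and they permit rather than require it to come before the procedure. A fed breath on another day is not ruled out, so the point about order and sedation applies only to a same-day scheme.

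**The bias may be small.** At a shift of 1.0 or 1.5 standard deviations, role alone would rarely pass the assumed rule, and the protocol gives no information on the shift. This is correct, and the conclusion does not rest on those figures.

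**It is only a pilot.** The template waives power analyses and endpoints for pilots. It does not waive saying who supplies one of the two classes being compared.

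**Narrowing the conclusion leaves the purpose unserved.** This is fair. Signals from companions who already happen to be fasting would fill one empty cell and separate state from role among companions. Carrying that result to patients would need a further assumption that the food effect is the same in both groups.

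**Conclusion.** The concern holds. The contradiction is in the current text and changes the headcounts: 25 versus 50 people for the pilot, 250 versus 500 for the full study.

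The confounding is conditional. If companions are the only non-fasting source, it is complete in both training and test, and accuracy by itself cannot support a conclusion about fasting state. If the scheme is same-day pairing with fasting always first, order and usually sedation replace role as the confounder. Until the protocol says which scheme applies, the conclusion that the trial can support is undefined.

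The size of any bias cannot be determined from the documents. The stated figure of about 450 was not needed here; it cannot be verified because no null value or precision is given.

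**What to change.** - **Choose one scheme.** Reconcile Purpose, Subject Information, Study Design and Statistical Considerations on whether the comparison is within or between persons. Make the population line, inclusion criteria 2 and 4 and exclusion criterion 1 agree with it.
- **Count people and signals separately.** Separate persons: pilot 50 people, full study 500. Paired: pilot 25 people, full study 250 (200 training, 50 test) for the same 500 signals.
- **If within-person,** split training and test by person, and state how fasting state is separated from order, time and sedation. Recording these is not enough if they coincide fully with state. Apply the design to training as well as test, because pairing the test set alone leaves the model trained on confounded data.
- **If between-person with companions as the only non-fasting source,** restate the primary conclusion as discrimination of fasting patients from non-fasting companions, not of fasting state.
- **In either case,** record role and time since last food or drink for every participant, companions included.

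No fasting instruction needs to change.

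**Cost.** A text amendment and a short questionnaire. The between-person option needs no extra breath tests but narrows the claim. The within-person option adds a second 5-minute breath per participant and an account of order and sedation. Either headcount, 250 or 500, fits the stated accrual of 1000.
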